Secondary Objectives:

Device success, procedural success, angioplasty outcomes, MACE at 6/12 months, TLR at 6/12 months, SAEs, MACE-free survival.

Endpoints:

Primary Endpoint:

MACE at 30 days.

Secondary Endpoints:

Device success, procedural success, post-usage angioplasty results, MACE at 6/12 months, TLR, TVR, SAEs, MACE-free survival.

Study Population:

Sample Size: 360 subjects

Inclusion/Exclusion criteria:

Inclusion Criteria:

Those subjects eligible for and who met the following inclusion/exclusion criteria were enrolled in this study.

1. Adults ≥ 18 yrs,
2. Clinical indication for PCI
3. suitable lesion for DCB-only strategy
4. small vessel disease
5. Patient has clinical evidence of ischemic heart disease or a positive functional study
6. Patient and his or her treating physician agree that the patient will comply with all the required post-procedure follow-up.

7. One or more target lesions require treatment

Exclusion Criteria:

Patients were excluded if **ANY** of the following conditions apply:

1. Patient has active infection
2. STEMI <72 hrs, LM disease,
3. heavy calcification, thrombus-rich lesions,
4. mandatory stent requirement,
5. sirolimus allergy, pregnancy,
6. Concurrent medical condition with a life expectancy <1 yr
7. Clinically relevant contraindication to aspirin, heparin, clopidogrel bisulphate, or ticlopidine including thrombocytopenia, neutropenia, or leukopenia
8. Active peptic ulcer or upper gastrointestinal bleeding.
9. Current participation in an investigational drug or device trial that has not completed its primary endpoint follow-up period.
10. Pregnancy or woman of childbearing potential who, in the opinion of the investigator, does not take adequate measures to prevent conception

Study Design:

Comparative Arm: None (no randomization)

Centers: Multicenter – Malaysia, Myanmar

Study Duration: 12 months follow-up per patient

Introduction

The Mamba Rapid Exchange Sirolimus Coated Dilatation Catheter is a rapid exchange, PTCA catheter with a balloon located at its end designed for Transluminal angioplasty by percutaneous way. This catheter includes distally two coaxial lumens with a balloon located at the tip. One lumen is used for inflation of the balloon and the other permits the use of guide wire (0.014" max) to facilitate the advancement of the catheter to and through the stenosis to be dilated. The MAMBA Rapid Exchange Sirolimus Coated Dilatation Catheter has flexible distal shaft with a hydrophilic coating on its outer body. The balloon has two Platinum-Iridium radiopaque marker bands, one at each end of the balloon, which represents the approximate balloon working length at nominal pressure for correctly positioning the balloon under fluoroscopy.

Mamba is a Sirolimus Coated Dilatation Catheter for the treatment of coronary artery disease, indicated for In-Stent Restenosis, Small Vessels and Bifurcation Lesions. Sirolimus Coated Dilatation Catheter (DCB) is a novel device for Percutaneous Coronary Intervention (PCI), which has demonstrated favorable outcome due to its peculiar characteristic of a high-concentration, rapid local delivery of an anti-restenotic drug without the use of a durable polymer or metal stent.

[figure not shown]
Drug Sirolimus

[figure not shown]
Mamba Sirolimus Drug Eluting PTCA Catheter has a drug loading of 2.75 $\mu\text{g}/\text{mm}^2$ of balloon surface area coated with Sirolimus as the active anti-proliferative agent.

Mechanism of Action for Sirolimus:

The mechanism by which the Sirolimus Coated Dilatation Catheter inhibits neointimal growth as seen in pre-clinical and clinical studies has not been established. At the cellular level, Sirolimus inhibits growth factor-stimulated cell proliferation. At the molecular level, Sirolimus forms a complex with the cytoplasmic protein FKBP-12 (FK 506 Binding Protein). This complex binds to and interferes with FKBP-12 Rapamycin Associated Protein (FRAP), also known as the mammalian target of rapamycin (mTOR), leading to inhibition of cell metabolism, growth, and proliferation by arresting the cell cycle at the late G1 stage.

It inhibits growth factor & cytokine-stimulated cell proliferation. DNA damage checkpoint (G1 check):chk1-kinase inactivation before DNA replication and also inactivation of cdk2- cyclin a protein (growth factor).

Balloon

A balloon is made up of nylon material having PTFE coated stainless steel hypo tube shaft. Two radiopaque markers located underneath the balloon, fluoroscopically mark the working length of the balloon.

Available Sirolimus Drug Eluting PTCA Catheter Sizes

Diameters (mm)	Available Lengths (mm)									
1.50	06	08	10	12	15	20	25	30	35	40
2.00	06	08	10	12	15	20	25	30	35	40
2.25	06	08	10	12	15	20	25	30	35	40
2.50	06	08	10	12	15	20	25	30	35	40
2.75	06	08	10	12	15	20	25	30	35	40
3.00	06	08	10	12	15	20	25	30	35	40
3.50	06	08	10	12	15	20	25	30	35	40
4.00	06	08	10	12	15	20	25	30	35	40

Study rationale

This is a multi-center; prospective study aimed at evaluating the safety and effectiveness of the Mamba Sirolimus Drug Eluting PTCA Catheter in reducing neointimal hyperplasia and decreasing restenosis during PCI of stenotic coronary artery disease as well as intermediate-term outcomes. High Radial Strength, Excellent conformability, and Sirolimus eluting characteristics. A Drug Eluting PTCA Catheter of this type is expected to decrease restenosis following PCI and thereby improve Clinical Outcomes.

Study Procedure:

Baseline evaluation, index PCI procedure, device success, procedural success, post-angioplasty results. Follow-up at 1, 6, 12 months (clinical only).

Screening and eligibility check

Informed consent

Baseline assessment (demographics, ECG, labs, angina class)

Index DCB procedure (balloon angioplasty using Sirolimus-coated DCB)

Pre-dilatation of the target lesion with an appropriate semi-compliant or non-compliant balloon is mandatory. Only lesions with successful pre-dilatation—defined as TIMI 3 flow, no flow-limiting dissection, and $\leq 30\%$ residual stenosis—are eligible for DCB deployment."

No stent implantation unless medically necessary (bailout)

Discharge as per hospital protocol

Follow-up visits at 1, 6, and 12 months for clinical evaluation, ECG, and adverse event assessment

Follow-Up Schedule:

Timepoint	Visit Type	Assessments
Day 0	Baseline	Demographics, consent, eligibility, angina class, ECG, labs
Day 1	Procedure	DCB implantation, procedural outcomes
1 Month	Clinic visit	MACE, adverse events, ECG, medication adherence
6 Months	Clinic/Tele	MACE, TLR, adverse events, angina class
12 Months	Final visit	MACE, TLR, SAE reporting, device durability

Data Management and Monitoring:

Use of Electronic Data Capture (EDC)

On-site and remote monitoring

Centralized adjudication of endpoints by Clinical Events Committee (CEC)

Safety reviewed periodically by an independent Data Monitoring Committee (DMC) if required

Ethics and Regulatory Compliance:

Conforms to ISO 14155:2020 and Declaration of Helsinki
Ethics Committee/IRB approvals mandatory at each site
Adverse events reported to regulatory bodies per local laws
Fully anonymized patient data to protect confidentiality

Statistical Analysis Plan (SAP):

ITT and PP populations.
Descriptive statistics for baseline and outcome data
95% CI for MACE. Kaplan–Meier for survival
Exploratory subgroup analysis.
No formal hypothesis testing due to non-comparative design

Subgroup analysis

No subgroup analyses are planned.

Withdrawal, discontinuation, and/or replacement of subjects

All patients have the right to withdraw at any point during the period of the clinical study. It will be documented whether or not each patient completed the clinical study. Every attempt should be made to collect follow-up information. Discontinued patients will not be replaced.

Safety Reporting

AE, SAE, and device deficiency reporting according to ISO 14155.

Adverse Events Reporting

Definitions

At each evaluation, the investigator will determine whether any adverse events (AEs) have occurred. For the purpose of this protocol, an adverse event is any undesirable clinical occurrence in a subject that can be attributed to the device, Sirolimus Drug Eluting PTCA Catheter, procedure, or medications required by this protocol (i.e., Aspirin, Clopidogrel Bisulfate [Plavix®], or other antiplatelet medication).

The following **Anticipated Events** have been

identified as possible complications of Sirolimus Drug Eluting PTCA Catheter procedure:

1. Allergic/immunologic reaction to anticoagulant and/or antithrombotic therapy
2. agents or contrast medium
3. Aneurysm
4. Arrhythmia's (bradycardia, rhythmical disturbances)
5. Arterial perforation
6. Bleeding complications
7. Cardiac tamponade
8. Cardiogenic shock
9. Death
10. Dissection

11. Drug reactions to antiplatelet agents/ anticoagulation agents/contrast medium
12. Emboli (tissue, air or thrombic emboli)
13. Embolization
14. Emergency CABG
15. Entry site complications
16. Fever
17. Fistulization
18. Heart Failure
19. Hemorrhage (hematoma)
20. Hypotension/hypertension
21. Infection (and pain at insertion site)
22. Myocardial infarction
23. Myocardial ischemia
24. Nausea and vomiting
25. Occlusion
26. Palpitations
27. Perforation or rupture
28. Pericardial effusion
29. Prolonged angina
30. Pseudoaneurysm
31. Renal failure
32. Respiratory Failure
33. Restenosis of the stented segment
34. Rupture of native coronary artery
35. Shock/pulmonary oedema
36. Stroke
37. Thrombosis (acute, subacute or late)
38. Unstable Angina Pectoris
39. Vascular complications, which may require vessel repair
40. Ventricular fibrillation
41. Vessel spasm

The following **Anticipated Events** have been identified as possible complications of Sirolimus coating:

1. Allergic/immunologic reaction to drug coating
2. Alopecia
3. Anemia
4. Blood product transfusion
5. Gastrointestinal symptoms
6. Hematologic dyscrasia (including leukopenia, neutropenia, thrombocytopenia)
7. Hepatic enzyme changes
8. Histologic changes in vessel wall, including inflammation, cellular damage or necrosis
9. Myalgia/Arthralgia

10. Peripheral neuropathy

The following **Anticipated Events** have been identified as possible complications of the medicine

Sirolimus:

1. Change in taste
2. Change in color of the nails
3. Change in normal bowel habits for more than 2 days
4. Chest pain
5. Chills
6. Cough
7. Difficulty swallowing
8. Dizziness
9. Facial flushing
10. Fatigue
11. Fever
12. Loss of appetite
13. Mouth blistering
14. Nausea and vomiting
15. Pain in the joints of the arms or legs lasting 2-3 days
16. Pain, redness, or swelling at the injection site
17. Severe exhaustion
18. Shortness of breath
19. Skin rash
20. Sore throat
21. Tingling in the hands or toes
22. Thinned or brittle hair
23. Unusual bruising or bleeding

Unanticipated Adverse Device Effects (ADEs) are defined as adverse effects on health or safety or any life-threatening problem or death caused by or associated with a device, if that effect, problem, or death was not previously identified in nature, severity or degree of incidence in the investigational plan or IDE application, or any other unanticipated serious problem associated with a device that relates to the rights, safety, or welfare of patients.

Adverse Event (AE): An adverse event is defined as any undesirable clinical event occurring to a subject, during a clinical study, whether or not considered related to the investigational product(s).

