Clinical circumstances in which unstable angina occurs:

Class A: Secondary unstable angina. Patients in whom unstable angina develops secondary to a clearly identified condition extrinsic to the coronary vascular bed that has intensified myocardial ischemia. Such conditions reduce myocardial oxygen supply or increase myocardial oxygen demand and include anemia, fever, infection, hypotension, uncontrolled hypertension, tachyarrhythmia, unusual emotional stress, thyrotoxicosis, and hypoxemia secondary to respiratory failure.

Class B: Primary unstable angina. Patients who develop unstable angina pectoris in the absence of an extra cardiac condition that have intensified ischemia, as in class A.

Class C: Post infarction unstable angina. Patients who develop unstable angina within the first 2 weeks after a documented acute myocardial infarction

CABG: Coronary Artery Bypass Graft.

CCS (Canadian Cardiovascular Society) classification

Class I: Ordinary physical activity, such as walking and climbing stairs, does not cause angina. Angina with strenuous, rapid, or prolonged exertion at work or recreation.

Class II: Slight limitation of ordinary activity. Walking or climbing stairs rapidly, walking up hill, walking or stair climbing after meals, in cold, in wind, or when under emotional stress or during the first few hours after awakening may cause pain. Walking more than two blocks on the level and climbing more than one flight of stairs at a normal pace and in normal conditions.

Class III: Marked limitation of ordinary physical activity. Walking one-two blocks on a level and climbing one flight of stairs at normal pace results in angina.

Class IV: Inability to carry on any physical activity without discomfort. Anginal syndrome may be present at rest.

De novo lesion: A coronary lesion not previously treated.

Dissection NHLBI classification National Heart Lung and Blood Institute:

A – Intraluminal radiolucent defect

B – Extraluminal “cap” (without staining)

C – Extraluminal “cap” with persistence of dye (staining)

D – Spiral defects

E – Persistent filling defect

F – Filling defect with total occlusion

Note: Types E & F dissections may be caused by thrombus

DS (Diameter Stenosis):

Percent DS – Value calculated as $100 * (1 - (MLD/RVD))$. A 100 %DS is imputed for total occlusions.

Late loss:

Late lumen loss is defined as the difference in minimal lumen diameter (MLD) between post-procedural and follow-up in mm

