MACE (Major Adverse Cardiac Events):

Composite of Death (Both Cardiac & Non-Cardiac Death), MI (Q-wave and Non-Q-wave), (emergent)

CABG or clinically driven Target Lesion Revascularization (TLR).

Major vascular complications:

All pseudoaneurysms, vascular access site bleeding associated with a decrease in hemoglobin ≥ 3.0 mmol/L as well as vascular events which required surgical repair or transfusion of > 2 units within 30 days of the procedure.

MI (Myocardial Infarction):

Necrosis of the myocardium, as a result of interruption of the blood supply to the area, as in coronary thrombosis.

MI, non-Q-Wave:

Elevation of post-procedure CK levels to > 2 times normal with elevated CK-MB in the absence of pathological Q waves. If no assay for CK-MB was performed, elevation of CK levels to > 2 times normal without new Q waves is also considered a non-Q-wave MI.

MI, Q-Wave:

MI, Q-Wave Development of new, pathological Q waves in 2 or more contiguous leads (as assessed by the investigator and confirmed by the Clinical Endpoint Committee) with post-procedure CK-MB levels elevated above normal.

MLD (Minimal Lumen Diameter):

MLD (Minimal Lumen Diameter) Mean Minimal Lumen Diameter (mm).

Procedure success rate: Percentage of patients with angiographic success and without the occurrence of MACE during the index hospitalization.

QCA (Quantitative Coronary Angiography, off-line):

Off-line refers to assessment at the Angiographic Core Laboratory. The method is a quantitative estimate obtained with a digital angiographic computer utilizing an automatic edge detection algorithm.

RVD (Reference Vessel Diameter):

Interpolated reference diameter.

SAE (Serious Adverse Event):

An adverse event is defined as serious, whenever the adverse event is fatal, life-threatening, results in persistent or significant disability/incapacity, requires inpatient hospitalization or prolongation of hospitalization, results in fetal death or distress, is a congenital anomaly/birth defect and in cases of cancer/malignancy.

Stroke:

A focal neurological deficit, resulting from a vascular cause involving the CNS, of sudden onset that is not reversible within 24 hours (including death) and which is not due to a readily identifiable cause (i.e. brain tumor, trauma).

TLR (Target Lesion Revascularization):

Any repeat treatment of the stented segment including 5 mm proximal and 5 mm distal from the edge of the stent.

TVF (Target Vessel Failure):

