Cardiac Death, MI (Q-wave and non-Q-wave) or Target Vessel Revascularization (TVR) that could not be clearly attributed to a vessel other than the target vessel.

TVR (Target Vessel Revascularization):

Revascularization of any segment of the index coronary artery, which was in physical contact with any component (guiding catheter, guidewire, balloon catheter, etc.) of the angioplasty hardware during the initial procedure

TWS (Technician's Work Sheet):

Part of the CRF used to specify the details of the angiographic procedure and the angiographic observations.

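### TLR is defined by a stent that the intended balloon-only lesion does not have, so TLR and the TLR part of MACE, including the primary endpoint, are open to undercounting

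*Protocol*

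**What the plan says.** The only definition of TLR is in Appendix I of the Protocol: "Any repeat treatment of the stented segment including 5 mm proximal and 5 mm distal from the edge of the stent". The MACE entry there lists death from any cause, Q-wave and non-Q-wave MI and, after the word emergent in brackets, "CABG or clinically driven Target Lesion Revascularization (TLR". MACE at 30 days is the primary endpoint. MACE and TLR at 6 and 12 months are secondary, as are TVR and MACE-free survival.

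The lesions are chosen and treated without a stent in mind. The inclusion criteria ask for a "suitable lesion for DCB-only strategy", the exclusion criteria list "mandatory stent requirement", and Study Procedure permits a stent only as bailout. Study Procedure also makes pre-dilatation with a separate balloon compulsory before the DCB is used. The Introduction describes the device as "indicated for In-Stent Restenosis, Small Vessels and Bifurcation Lesions", so a target lesion might lie inside an older stent; the eligibility criteria neither require nor rule this out.

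TVR is defined without reference to a stent: "Revascularization of any segment of the index coronary artery, which was in physical contact with any component (guiding catheter, guidewire, balloon catheter, etc". Data Management and Monitoring gives endpoint adjudication to a central CEC.

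Separately, Study rationale says that the study evaluates safety and effectiveness "in reducing neointimal hyperplasia and decreasing restenosis during PCI of stenotic coronary artery disease as well as intermediate-term outcomes".

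**The concern.** The TLR rule is written for a stent, and the study treats with a balloon. If there is no stented segment and no stent edge, the rule has nothing to apply to. A committee that follows the text cannot count a repeat procedure on such a lesion as TLR. A committee that counts it is following a rule that is not written down.

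The matter is more than tidiness because TLR feeds other endpoints. It is a secondary endpoint itself, and through its clinically driven form it enters MACE at 30 days, 6 months and 12 months. From there it reaches MACE-free survival and procedural success, which Appendix I defines partly by the absence of MACE in hospital. The study is meant to support a clinical evaluation report, and any undercount would flatter the device.

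**Working it through.** The Protocol gives no figure to reproduce on this point. The check sets the definition against each kind of target lesion that the Protocol allows.

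| Target lesion after the index procedure | Stented segment? | Can repeat treatment be TLR as written? |
|---|---|---|
| Balloon only, no earlier stent (the intended case) | No | No |
| Balloon plus bailout stent | Yes | Yes, but only in the stent and within 5 mm of it; vessel treated by balloon beyond that is left out |
| Balloon inside an older stent, if such lesions are enrolled | Yes, from an earlier procedure | Yes, with the same limit |

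**Effect on MACE.** Count subjects at a given time point. Let L be the subjects whose only qualifying event by then is a clinically driven TLR that the text does not cover. Then

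MACE as written = MACE as intended − L.

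A subject with an uncovered TLR who also dies, has an MI or needs emergent CABG by that time point is still counted. So L cannot exceed the number of subjects with an uncovered TLR, and it is smaller as soon as one of them has another component. In MACE-free survival such a subject is kept as an event but may be given a later event time.

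**Does TVR fill the gap?** In part. Its definition includes contact with the balloon catheter, so a repeat procedure on a balloon-only lesion falls under TVR. But TVR is not a component of MACE, so it does not restore the primary endpoint. It also works at the level of the vessel and cannot stand in for TLR.

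**Size.** Let s be the share of treated lesions with a stent and r the ratio of TLR risk in stented to balloon-only lesions. Ignoring the partly covered segments in the second and third rows of the table, the share of TLR counted under a literal reading is

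r·s / (r·s + 1 − s).

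Neither s nor r is in the Protocol. Purely as assumptions:

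- s = 5%, r = 1: 0.05 / (0.05 + 0.95) = 5.0% counted, 95.0% missed.
- s = 30%, r = 2: 0.60 / (0.60 + 0.70) = 46.2% counted, 53.8% missed.

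At r = 1 the missed share is 1 − s, which is the assumption handed back. These figures show how the rule behaves if applied to the letter. They do not estimate what will happen in this study.

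**The rationale.** Neointimal hyperplasia and angiographic restenosis need imaging at follow-up. Study Procedure makes the visits at 1, 6 and 12 months clinical only. Appendix I has an entry stating "Late lumen loss is defined as the difference in minimal lumen diameter (MLD) between post-procedural and follow-up in mm", but no objective or endpoint uses it. There is no comparative arm, and the Protocol's SAP section rules out formal testing. The words for reduction and decrease therefore have nothing behind them, but the sentence drives no endpoint or analysis either.

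**The case against.** The best defence is that nobody would read the definition literally. The Follow-Up Schedule records TLR at 6 and 12 months in a balloon study, a central committee adjudicates, and a literal reading would empty the Protocol's own endpoint for most intended lesions. The list of anticipated events also speaks of restenosis of a stented segment, which suggests inherited stent wording and not a deliberate restriction. The realistic harm is then ambiguity, not the loss of most events. Much of this stands: the likely result is that the committee reads in the intended meaning.

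It does not dispose of the point. Appendix I holds the Protocol's only TLR definition, so the count would rest on an unwritten convention. Good will also does not fix the boundary. Once the stent edge is gone, the 5 mm could be measured from the DCB or from the pre-dilatation balloon, and these need not cover the same length. Two adjudicators with the same intent could classify the same event differently.

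A reader might infer two stronger things. One is that the study cannot assess restenosis at all, so that its aim fails. The documents do not support this: the formal objectives are descriptive, TLR and TVR record clinical restenosis, and only the neointimal and angiographic measures are missing. The other is that most TLR events will be lost. That needs a literal committee and a stent rate that the Protocol does not give. Confidence intervals for a full and a reduced count would not help, since both counts come from the same 360 subjects.

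**Conclusion.** The TLR definition is wrong as written for this study. For a balloon-only lesion without an earlier stent it can never be met, and the fault reaches the primary endpoint through the clinically driven TLR component of MACE. Undercounting follows unless the CEC departs from the text. The direction is clear, because the stent wording can only remove events relative to a rule based on the treated segment. The size cannot be derived from the documents, and it is smaller in MACE than in TLR to the extent that other MACE components occur in the same subjects. The conclusion rests on the text alone and on no assumed rate.

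The rationale sentence is a minor drafting mismatch, since the objectives and the planned analysis are already descriptive.

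**What to change.** Define TLR as any repeat treatment of the target-lesion segment treated at the index procedure, plus 5 mm proximal and 5 mm distal. State that this segment is the full length covered by the pre-dilatation balloon, the DCB and any bailout or pre-existing stent in that lesion. Naming all of these matters, because a reference to the balloon-treated segment alone would not say which balloon sets the margins.

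Use this one definition for the TLR endpoint, for the TLR component of MACE and for CEC adjudication, in all subjects. Re-adjudicate any event already judged under the present text, and disclose the change.

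In Study rationale, replace the language of reduction with a descriptive aim that matches the objectives, or state that neointimal hyperplasia and angiographic restenosis are not measured at follow-up.

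The cost is a dated protocol amendment with matching CRF and CEC wording, possible re-adjudication, and perhaps a slightly higher reported event rate. No new visit, procedure or patient is needed. The eligibility text is in the past tense, so enrolment may have begun; the date of the amendment should therefore be reported with the results.
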